**C. Study Design and Research Methods**

**Design:** The proposed project is a randomized controlled trial to determine if the hospice specific PtDA improves hospice knowledge, opinions of hospice, and decision self-efficacy in a nationally representative cohort of 400 Black adults aged 65 years or older.

**Aim 1** consists of a baseline measurement of hospice knowledge, opinions of hospice, and decision self-efficacy (survey instruments described above) in making decisions about hospice care. A total of 400 participants will be enrolled at baseline and complete the baseline surveys.

**Aim 2** Upon completion of the baseline assessment, 200 participants will be randomly assigned to review the hospice PtDA. The hospice PtDA exists as a 12-page booklet. The PtDA is available here: <https://patientdecisionaid.org/hospice/>. The control group will not view the PtDA and will be asked to review an attention control activity similar to the hospice PtDA but about dementia care not hospice. The attention control activity is a 8-page booklet that is available here <https://patientdecisionaid.org/wp-content/uploads/2022/07/Dementia-Support-Tool- FINAL 6.1.2022.pdf>. All participants will be contacted approximately 30 days after the baseline assessments to complete the follow-up surveys. Participants will receive \$5 for completing the baseline visit and an additional \$5 for completing the 30-Day Follow-Up for a total of \$10 for completing the study.

**Aim 3** consist of up to 20 qualitative interviews with participants in the intervention arm who saw the hospice decision aid. The purpose of this aim is to evaluate the PtDA for appropriateness and acceptability. The PtDA was intentionally designed to be general and not culturally tailored to any specific group or disease process. These interviews will provide data on any modifications or revisions that may make the decision aid more appropriate for use in a population of older black adults. Individuals completing the interviews will receive a \$25 gift card.

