#### **D. Description, Risks and Justification of Procedures and Data Collection Tools:**

#### **E. Potential Scientific Problems:**

#### **F. Data Analysis Plan:**

**Aim 1:** To assess baseline hospice knowledge, opinions about hospice, and decision self-efficacy in a nationally representative sample of Black adults aged 65 and older.

**-Quantitative Analysis:** To achieve an alpha of 0.05 and a modest effect size of 0.3, a power analysis completed in SPSS yielded a required sample size of 139 individuals per group. Thus, the project will recruit a total of 400 participants (200 per group) to account for potential losses to follow-up. The literature on SDM and PtDAs varies in what is an acceptable effect size for increasing patient knowledge with PtDA interventions from 10% to 65%. I hypothesize that baseline knowledge will be low in this sample and based on the results of my prior work I am proposing a modest effect size of 0.3 for this project. Differences in mean scores between socioeconomic variables (e.g., income, education, zip code) and location (e.g., urban vs rural) will be evaluated using independent t-tests or  $\chi^2$  where appropriate. Additionally, multiple regression models will be used to assess differences between and within groups.

**Aim 2:** To evaluate the effect of the hospice PtDA on changing hospice knowledge, opinions of hospice, and decision self-efficacy in a population of Black and White adults aged 65 and older.

**-Quantitative Analysis:** Differences will be evaluated both between and within groups using paired and independent t-tests, respectively. Additionally, multiple regression models will be used to assess differences between groups pre/post-test.

**Aim 3:** To further understand the specific barriers to hospice enrollment and to elicit feedback about the appropriateness and acceptability of the PtDA I will conduct qualitative interviews with a subset of up to 20 participants in the intervention group who reviewed the PtDA.

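### Aim 2 leads with unadjusted t-tests while allowing for up to 30.5% loss; a baseline-adjusted regression should be the primary between-arm analysis

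*Combined protocol and SAP*

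**What the plan says.** Study Design and Research Methods has all 400 participants complete baseline surveys before 200 are randomised to the hospice PtDA and the rest to a dementia booklet. There is one follow-up: "All participants will be contacted approximately 30 days after the baseline assessments to complete the follow-up surveys".

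The sample size is justified under Aim 1 of the Data Analysis Plan. It uses an alpha of 0.05 and an effect size of 0.3, and it "yielded a required sample size of 139 individuals per group". The plan continues: "Thus, the project will recruit a total of 400 participants (200 per group) to account for potential losses to follow-up". No loss rate is stated.

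For Aim 2 the analysis is: "Differences will be evaluated both between and within groups using paired and independent t-tests, respectively". Read literally, that sentence assigns the paired test to the between-group comparison and the independent test to the within-group one. I take the reverse to be meant. The next sentence adds multiple regression models for between-group pre/post differences. It names no covariates, model form or priority over the t-tests. The documents define no analysis set, missing-data method, sensitivity analysis or primary Aim 2 analysis.

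**The concern.** The plan treats loss to follow-up as a matter of numbers only. The leading analysis is valid after loss only if those who remain are still comparable between arms on what predicts the outcome. The arms read different material (a 12-page hospice booklet or an 8-page dementia booklet) and then answer a remote survey 30 days later for $5. Interest and burden could differ by arm, and people who know little about hospice could leave at different rates.

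The plan also does not say whether the between-arm t-test is on the 30-day score or on change. Under baseline-related loss these two tests err in opposite directions, so the same data could support two different readings of the PtDA effect.

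**Working it through.** **1. The plan's own figure.** Inputs from the plan: alpha 0.05, effect 0.3 (taken as a standardised difference, SD = 1), 139 per group. Power and sidedness are not stated. With n = 2(z_alpha + z_beta)²/d²:

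- One-sided, 80% power: 2(1.645 + 0.842)²/0.09 gives 138; the t-distribution solution is 138.07, rounded up to 139.
- Two-sided, 70% power: the t-distribution solution is 138.12, also 139.
- Two-sided, 80% power: 175 (176 by the t-distribution), which does not reproduce the plan's figure.

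So 139 is reproducible.

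**2. Implied allowance for loss.** 1 - 139/200 = 30.5%. If two-sided 80% power was intended, it is only 1 - 176/200 = 12%.

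**3. Form of the bias.** Let D be the difference (PtDA minus control) in mean baseline score, in SD, among people who complete follow-up. Let rho be the baseline to follow-up correlation. If loss depends on baseline only:

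- bias of the t-test on 30-day scores = rho × D
- bias of the t-test on change scores = (rho - 1) × D

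**4. Size.** Loss rates, dropout slopes and rho are my assumptions, because the documents give none. Loss follows a logistic model in which low baseline scorers leave more often. The slope is the change in log-odds of loss per SD of baseline. D is found by numerical integration, and simulation gives the same biases to within about 0.004 SD.

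| Loss, PtDA / control | Slope, PtDA / control | D | 30-day bias, rho 0.5 / 0.7 | Change bias, rho 0.5 / 0.7 |
|---|---|---|---|---|
| 30.5% / 15% | 0.5 / 0.5 | 0.072 | +0.04 / +0.05 | -0.04 / -0.02 |
| 30.5% / 15% | 1.0 / 1.0 | 0.124 | +0.06 / +0.09 | -0.06 / -0.04 |
| 30.5% / 15% | 1.0 / 0.5 | 0.184 | +0.09 / +0.13 | -0.09 / -0.06 |
| 30.5% / 15% | 1.0 / 0 | 0.257 | +0.13 / +0.18 | -0.13 / -0.08 |
| 30% / 30% | 0.7 / 0 | 0.192 | +0.10 / +0.13 | -0.10 / -0.06 |
| 20% / 15% | 0.5 / 0.5 | 0.0235 | +0.01 / +0.02 | -0.01 / -0.01 |
| any | 0 / 0 | 0 | 0 | 0 |

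In the first three rows the 30-day bias is 12% to 43% of the planned 0.3 (0.036/0.3 to 0.129/0.3). In the 20% / 15% row it is about 4% to 6%. If high scorers left more often, all signs would reverse.

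**5. Baseline adjustment.** Regression of the 30-day score on arm and baseline, in completers only, was within 0.003 SD of the true effect in the simulated scenarios with baseline-related loss, which is simulation noise. In 300 simulated trials of 200 per arm at rho 0.5, a likelihood model using all 400 gave the same estimate as completers' ANCOVA to seven decimals.

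**6. Loss driven by the follow-up score.** Assume 20% loss in control, 40% in the PtDA arm, and loss in the PtDA arm related to the follow-up score (slope 0.7). Against a true 0.30, the t-test gives 0.55 and the adjusted estimate 0.43 to 0.49. Adjustment reduces this bias but does not remove it.

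**7. Precision.** ANCOVA multiplies the variance by 1 - rho², that is 0.75 at rho 0.5 and 0.51 at rho 0.7. With 139 per arm and a two-sided test, power for 0.3 rises from about 70% unadjusted to 82% and 94%.

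**The case against.** The strongest reply is that the plan already includes regression for pre/post differences between groups. If that model contains the baseline score, it removes the baseline-related bias shown above, completers or not. This is correct about the method. The plan does not say that baseline is a covariate, however, or that the regression takes precedence over the t-tests named first.

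A second reply is that the larger biases rest on unfavourable inputs. The control booklet is described as similar to the PtDA and the follow-up payment is the same in both arms, so loss may differ little. That also stands: the milder case gives a bias of little consequence, and no observed loss data exist.

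A reader might infer three stronger points, which are not supported:

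- *Unequal dropout by itself biases the effect.* It does not. Loss unrelated to score gives zero bias however unequal the rates, while equal rates with different mechanisms can bias the t-test.
- *Analysing completers is the defect, and keeping all 400 is the cure.* The documents never say that only completers are analysed; it follows from using a t-test. With one follow-up and baseline as the only predictor, a model on all 400 gives the same estimate as completers' ANCOVA.
- *The trial expects 30.5% loss.* That figure is derived from 139 and 200. It is a planning allowance, not a stated rate.

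**Conclusion.** The point holds in a limited form. The weakness is reliance on unadjusted t-tests when loss may relate to baseline score and differ between arms, with a better analysis available from data already planned for all 400. Under the assumed 30.5% versus 15% loss, slopes of 0.5 to 1.0 and correlation 0.5 to 0.7, the bias is +0.04 to +0.13 SD on 30-day scores and -0.02 to -0.09 SD on change scores. It reaches +0.18 SD on 30-day scores if loss depends on baseline in the PtDA arm only. It is about +0.01 to +0.02 SD on 30-day scores in the milder case, and zero if loss is unrelated to score. This is a risk that the plan leaves open, not a demonstrated bias.

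The finding that ANCOVA removes the bias assumes that loss depends on baseline only, and that the relation of follow-up to baseline is linear with the same slope in both arms, as in the calculations.

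**What to change.** - **Primary analysis.** For each Aim 2 outcome, make the between-arm analysis a regression of the 30-day score on randomised arm, adjusted for the baseline value of that score. State the analysis set (all randomised participants with a 30-day score, in the arm assigned) and the missing-at-random assumption. Keep the t-tests as descriptive, and correct which test serves which comparison.
- **Optional extension.** Use a likelihood model or multiple imputation that brings in other baseline variables, such as education, income and urban or rural location. This is worthwhile only if they predict loss or outcome. The documents do not show that they predict loss, and they do not expressly place the Medical Mistrust Index at baseline, so confirm that before using it.
- **Reporting.** Give loss by arm, with baseline scores of completers and non-completers in each arm.
- **Sensitivity.** Add one delta-adjusted analysis, for example with PtDA non-completers 0.1 to 0.3 SD worse than predicted, because baseline adjustment does not fix loss driven by the follow-up score.

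The cost is a few sentences in the plan and modest programming, with no extra participants or data. It is not free of assumptions: the primary result would rest on missing at random, which the sensitivity analysis probes.

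### Aim 2 names no primary analysis of the decision-aid effect and does not commit to adjusting for the baseline scores it collects before randomisation

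*Combined protocol and SAP*

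**What the plan says.** The Aim 2 quantitative plan in section IV.F (Data Analysis Plan) is two sentences long. The first reads "Differences will be evaluated both between and within groups using paired and independent t-tests, respectively". The second reads "Additionally, multiple regression models will be used to assess differences between groups pre/post-test". Neither is called primary. The aim itself is worded as "To evaluate the effect of the hospice PtDA on changing hospice knowledge, opinions of hospice, and decision self-efficacy", which fits either a 30-day comparison or a comparison of changes. The regression is given no outcome variable and no covariates.

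Section IV.C (Study Design and Research Methods) fixes the order of events. Under Aim 1, "A total of 400 participants will be enrolled at baseline and complete the baseline surveys"; these surveys cover hospice knowledge, opinions (HBAS) and decision self-efficacy (DSE). Under Aim 2, "Upon completion of the baseline assessment, 200 participants will be randomly assigned to review the hospice PtDA". The follow-up surveys come about 30 days after baseline in both arms.

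The Outcome Measures section (IV.A) lists the instruments without ranking them. No other section names a primary Aim 2 analysis or a baseline covariate.

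**The concern.** There are two separate issues.

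- **Undesignated analysis.** The text allows at least three analyses of the same randomised contrast: a t-test on 30-day scores, a t-test on change scores, and a regression that may or may not include baseline. They can disagree. If the choice is made after the data are seen and the favourable result is reported, the chance of a false positive for that outcome exceeds 5%.
- **Unused baseline information.** The baseline score of each outcome is a true pre-randomisation covariate. In large samples, ANCOVA on it is never less efficient than either t-test. A change-score t-test is less efficient than ignoring baseline when the correlation is below 0.5. This is a matter of precision: both t-tests are unbiased under randomisation.

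The t-test sentence adds to the uncertainty. Read literally, its closing *respectively* assigns the paired test to the between-group comparison and the independent test to the within-group one. The reverse is presumably meant.

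**Working it through.** **Inputs from the protocol (IV.F).** The basis is "To achieve an alpha of 0.05 and a modest effect size of 0.3", giving 139 per group, with 200 per group recruited to allow for losses. Power and sidedness are not stated.

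**Assumptions, not in the documents.** The 0.3 is a mean difference in units of the 30-day SD; SDs are equal at both visits; the test is two-sided; the baseline to 30-day correlation r is 0.3, 0.5 or 0.7.

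**Step 1: the plan's own figure.** The two-sample t-test sample size for d = 0.3 and alpha 0.05 is 138.07 (rounds up to 139) for one-sided 80% power, and 138.12 (also 139) for two-sided 70% power. Two-sided 80% power needs 176. So 139 reproduces, but under a two-sided test it corresponds to about 70% power for an unadjusted comparison.

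**Step 2: effective effect size under each permitted analysis.**

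- 30-day t-test: d = 0.3 at any r.
- Change-score t-test: d / √(2(1 − r)). At r = 0.3 this is 0.3 / √1.4 = 0.254; at 0.5, 0.300; at 0.7, 0.3 / √0.6 = 0.387.
- ANCOVA: d / √(1 − r²). At r = 0.3 this is 0.3 / √0.91 = 0.314; at 0.5, 0.3 / √0.75 = 0.346; at 0.7, 0.3 / √0.51 = 0.420.

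**Step 3: power.** Noncentral t with noncentrality (effective d) × √(n/2), on 2n − 2 degrees of freedom (2n − 3 for ANCOVA). For example, the 30-day t-test at n = 139 has noncentrality 0.3 × √69.5 = 2.50 and power 70.3%.

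| n per arm | Analysis | r = 0.3 | r = 0.5 | r = 0.7 |
|---|---|---|---|---|
| 139 | 30-day t-test | 70.3% | 70.3% | 70.3% |
| 139 | Change-score t-test | 55.8% | 70.3% | 89.6% |
| 139 | ANCOVA | 74.3% | 82.1% | 93.7% |
| 200 | 30-day t-test | 84.9% | 84.9% | 84.9% |
| 200 | Change-score t-test | 71.5% | 84.9% | 97.2% |
| 200 | ANCOVA | 88.0% | 93.3% | 98.7% |

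The gain of ANCOVA over the 30-day t-test is 3 to 4 points at r = 0.3, 8 to 12 points at r = 0.5 and 14 to 23 points at r = 0.7.

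**Step 4: precision.** The 95% CI half-width in SD units is t(0.975) × √(2/n) × √(1 − r²). At 139 per arm it is 0.236 unadjusted, and 0.225, 0.205 or 0.169 with ANCOVA at r = 0.3, 0.5 or 0.7. At 200 per arm it is 0.197 unadjusted, and 0.188, 0.170 or 0.140 with ANCOVA.

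**Step 5: false positives if the best result is chosen.** Simulation with no true effect, bivariate normal scores, 100,000 trials per cell. Each test alone rejected in 4.8% to 5.1% of trials. The table gives the chance that at least one is significant.

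| Analyses tried | n per arm | r = 0.3 | r = 0.5 | r = 0.7 |
|---|---|---|---|---|
| 30-day t-test, ANCOVA | 139 | 6.4% | 7.2% | 8.1% |
| 30-day t-test, ANCOVA | 200 | 6.4% | 7.4% | 8.3% |
| Those two plus change-score t-test | 139 | 9.1% | 9.4% | 9.8% |
| Those two plus change-score t-test | 200 | 9.2% | 9.7% | 10.1% |

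**The case against.** The best defence is that the plan is less silent than it looks. Regression for pre/post differences most naturally means a model using both scores, which could well be ANCOVA, and listing t-tests first suggests an order. This is fair, but the same wording also covers a change-score or group-by-time model. Even if ANCOVA is meant, it is introduced as an addition to the t-tests, with no rule for which result answers Aim 2.

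Other points stand as limits on the size of the concern:

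- An unadjusted comparison in a randomised trial is not an error. That part of the concern is about efficiency only.
- The power figures depend on an assumed r and on a two-sided test. If a one-sided 5% test was intended, the unadjusted t-test at 139 per arm has 80.2% power, and ANCOVA has 83.4%, 89.2% or 96.8%. Also, 139 per arm is reached only after a loss of 1 − 139/200 = 30.5%; at 180 per arm the two-sided unadjusted power is already 81.0%.
- The false-positive figures describe what happens if the best result is picked. Nothing in the protocol says it will be. The three-test figure also counts a change-score t-test that the plan permits but does not name, so 6.4% to 8.3% is the more cautious figure.
- Naming any single between-arm analysis in advance would remove the selection risk. ANCOVA is preferred because it is also the most precise of the three.

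**Conclusion.** The concern holds. Aim 2 has no designated primary analysis and no commitment to baseline adjustment, although the baseline scores will be in hand before randomisation. The lack of designation rests on the text alone. Its possible cost, 6.4% to 8.3% false positives per outcome for two analyses or 9.1% to 10.1% for three, is conditional on selective reporting.

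The efficiency gain depends on r. It is small at 0.3 and substantial at 0.7. At 139 per arm and two-sided 5%, ANCOVA passes 80% power by r = 0.5. If the 0.3 was already expressed in change-score or residual SD units, the power gains do not apply as shown, but the selection risk is unaffected. This should be corrected, but it does not make the trial invalid.

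**What to change.** Rewrite the Aim 2 quantitative paragraph in IV.F to state that:

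- for each of knowledge, HBAS and DSE, the primary analysis is a linear model of the 30-day score on randomised arm and the baseline score of the same measure;
- participants are analysed in the arm to which they were assigned;
- the result is reported as the adjusted mean difference with its 95% CI;
- the t-tests and any other regression are supportive only.

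In the same edit, correct the t-test sentence so that the independent test goes with the between-group comparison and the paired test with the within-group one.

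The cost is plan wording only: the baseline scores are already collected and regression is already planned. The change settles the choice of analysis within each outcome. It does not control error across three outcomes each tested at 5% (up to 1 − 0.95³ = 14.3% if independent), which needs its own statement.
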